## IRB Minimal Risk Protocol Template

**Note: If this study establishes a human specimen repository (biobank) for research purposes, do not use this template. Use the Mayo Clinic Human Specimen Repository Protocol Template found on the IRB home page under Forms and Procedures at <http://intranet.mayo.edu/charlie/irb/>**

**First-time Use:** Use this template to describe your study for a new IRB submission.

1. Complete the questions that apply to your study.
2. Save an electronic copy of this protocol for future revisions.
3. When completing your IRBe application, you will be asked to upload this document to the protocol section.

**Modification:** To modify this document after your study has been approved:

1. Open your study in IRBe. Click on the study 'Documents' tab and select the most recent version of the protocol. Save it to your files.
2. Open the saved document and activate "Track Changes".
3. Revise the protocol template to reflect the modification points , save the template to your files
4. Create an IRBe Modification for the study and upload the revised protocol template.

### Research Question and Aims

Hypothesis: Supplementing lidocaine/epinephrine injections with intralesional lidocaine jelly will decrease the overall quantity of lidocaine/epinephrine injectable used, and will decrease patients' self-reported pain/anxiety associated with needle sticks.

Objectives: To assess how using lidocaine jelly in Mohs surgery impacts 1) the overall quantity of lidocaine/epinephrine injectable needed to maintain anesthesia, and 2) patients' pain/anxiety associated with anesthesia injections.

### Background:

Mohs micrographic surgery is a procedure that removes cancerous lesions of the skin in a step-wise fashion. Patients are injected with local analgesia for tumor extirpation. The tumor is removed and the tissue is sent for histopathology while the patient waits. Tissue processing time can take up to 2 hours during which the effects of the local analgesia have waned. Once the tissue has been process and examined, patients are brought back to the surgical suite and either have another section of tissue removed (if the margins were positive) or have the wound reconstructed (if the margins were negative). Lidocaine Hydrochloride (Xylocaine) injection with

Epinephrine is the traditionally method used to maintain local anesthesia throughout the procedure. The FDA has declared a shortage of this injectable Lidocaine/Epinephrine, stressing the need for a substitute drug. Additionally, multiple needle sticks can be uncomfortable and anxiety provoking for patients. Needle sticks on hypersensitive areas such as the nose can be particularly painful. Previous research has demonstrated that a different form of anesthetic, a topical lidocaine jelly, is efficient in prolonging anesthesia in Mohs surgery (Robins, 1991). No study has published the impact of supplemental lidocaine jelly use on the overall quantity of injection needed, nor on patient pain/anxiety associated with needle sticks.

## Study Design and Methods

### Methods:

We will conduct a prospective, randomized trial of 250 patients receiving Mohs micrographic surgery to lesions on the nose. Annually Mohs micrographic surgery is performed on approximately 900 patients with 30% of these procedures being performed on lesions on the nose. Patients receiving Mohs treatment for lesions on the nose will be randomly assigned to one of two groups: (1) those whose wounds will be dressed with lidocaine jelly (treatment group), and (2) those whose wounds will be dressed with surgical lubricant (control/placebo group).

All patients will receive a pre-treatment baseline pain/anxiety survey followed by an initial lidocaine injection. The amount of lidocaine/epinephrine injection each patient receives throughout remaining stages of surgery will be recorded, as per the current workflow. All patients will complete a second pain/anxiety survey immediately after numbing but prior to the first stage of surgery.

After the first stage of surgery, either lidocaine jelly or surgical lubricant will be applied to the wound followed by a pressure bandage as per standard practice. Dressing are removed immediately prior to the next stage of surgery. After each subsequent stage of surgery, an identical wound dressing will be placed on the operative site.

Immediately prior to each subsequent stage of surgery, we will assess patients' pain sensation, and additional lidocaine/epinephrine will be injected if needed. After the surgical site is re-anesthetized, vital signs will be recorded and the Pain/Anxiety survey administered immediately prior to the first incision of that stage.

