### Power Statement:

Power simulations were based on anticipated analysis of group differences via *t*-tests, Chi-square tests, and Wilcoxon rank-sum tests. These simulations suggested that enrollment of 250 total patients (125 each in control/placebo group and lidocaine jelly treatment group) would allow us to detect a moderate effect ( $d = .5$ ,  $w = .3$ , and  $d=.5$  respectively) of differences between groups at a significance level of  $p < .05$  with power of 90% or greater in our planned analyses.

**Data Analysis Plan:** Primary analyses of interest are descriptive statistics for measures of pain, anxiety, biometric indicators (e.g., heart rate, blood pressure), and amount of total lidocaine administered by injection for each group. Secondary analyses will include statistical tests (e.g., *t*-tests,  $\chi^2$ , and Wilcoxon rank-sum) for comparison between control and treatment group for differences on pain, anxiety, and vital signs. Additional analysis of differences in pain/anxiety across repeated rounds of testing within groups will be explored given sufficient data via descriptive statistics, statistical test, and possible mixed models comparing changes over repeated rounds between groups (dependent on rates of patients with multiple-stage Mohs procedures).

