### Endpoints

**Primary:** patient pain/anxiety score as indicated by survey, and quantity of Lidocaine Hydrochloride (Xylocaine) Injection with Epinephrine

**Secondary:** Blood pressure and heart rate, any history of Mohs surgery (any location, any provider)

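### The post-dressing survey and vital signs are timed from re-anesthetizing the site, which happens only if needed, so patients whose anesthesia lasted may drop out of the pain/anxiety comparison

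*Combined protocol and SAP*

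**What the plan says.** Under Methods, before each stage after the first, "we will assess patients' pain sensation, and additional lidocaine/epinephrine will be injected if needed". The next sentence reads "After the surgical site is re-anesthetized, vital signs will be recorded and the Pain/Anxiety survey administered immediately prior to the first incision of that stage". Nothing says whether, when or about what a patient without a top-up is surveyed.

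The two earlier surveys, at baseline and after the initial numbing, are expressly for all patients. Both precede the first application of jelly or lubricant. The post-dressing survey carries no such wording.

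The hypothesis under Research Question and Aims is that the jelly "will decrease patients' self-reported pain/anxiety associated with needle sticks". Endpoints lists as primary both "patient pain/anxiety score as indicated by survey" and the quantity of injected lidocaine/epinephrine. The Data Analysis Plan names no survey time point for the between-group comparison and has no rule for a missing score.

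**The concern.** The jelly is meant to prolong anesthesia, so needing a top-up is itself an outcome of the randomised dressing. If only topped-up patients are surveyed, the pain/anxiety scores come from a subset chosen after randomisation, and the subset is smaller and more selected in the arm where the jelly works. The jelly-arm patients who remain are the more sensitive ones, so the comparison is tilted against the jelly and is no longer protected by randomisation.

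The only surveys guaranteed for everyone are taken before the dressing and cannot show its effect. The post-dressing survey is the only one that can.

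Surveying everyone leaves a smaller gap. The aim concerns pain and anxiety from needle sticks, and a patient with no injection at that return has no stick to rate. The plan does not say how that patient's answer is to be understood.

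**Working it through.** **1. The plan's own figure.** The Power Statement assumes "125 each in control/placebo group and lidocaine jelly treatment group" and a moderate effect (d = 0.5 for the t-test) at p < .05, "with power of 90% or greater in our planned analyses". Sidedness is not stated; two-sided is assumed here. The noncentrality is 0.5 / √(2/125) = 3.95, and noncentral-t power is 97.6%. The Wilcoxon test gives about 97%, and the chi-square test with w = 0.3 (noncentrality 250 × 0.3² = 22.5) gives 98.0% to 99.7% for 4 down to 1 degrees of freedom. The stated figure reproduces, so there is no arithmetic error. It presumes that all 125 per arm are scored.

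**2. Illustrative selection model.** The documents give no top-up rates and no correlation between need for a top-up and the survey score. Both are assumed.
- Latent sensitivity at return is N(0,1) in controls and N(−0.5,1) in the jelly arm. A patient is topped up above a common threshold c.
- The survey score has SD 1, correlation ρ with latent sensitivity within arm, and a true jelly benefit of 0.5 SD.
- Every randomised patient is assumed to have one post-dressing return.
- Only topped-up patients are scored.

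With φ and Φ the standard normal density and distribution function, let λ(q) = φ(q) / (1 − Φ(q)).

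**3. Control top-up of 70%.**
- Threshold: c = −0.524 for controls; relative to the jelly mean, q = −0.524 + 0.5 = −0.024.
- Jelly top-up rate: 1 − Φ(−0.024) = 51%.
- Scored: 125 × 0.70 = 87.5 and 125 × 0.51 ≈ 63.7, about 88 versus 64.
- λ is 0.3477/0.70 = 0.497 in controls and 0.3988/0.5097 = 0.782 in the jelly arm, a difference of 0.286 before rounding.
- Apparent benefit = 0.5 − 0.286ρ.
- Score variance among the scored = 1 − ρ²λ(λ − q). Power is from the noncentral t with the pooled SD.

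| ρ | Apparent benefit (SD) | Variance, control / jelly | Power |
|---|---|---|---|
| 1 | 0.21 | 0.49 / 0.37 | 50% |
| 0.5 | 0.36 | 0.87 / 0.84 | 64% |
| 0.3 | 0.41 | 0.95 / 0.94 | 73% |

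With ρ = 0 there is no bias, and the loss of numbers alone gives about 85.5%.

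**4. Other control top-up rates.**

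| Control / jelly top-up | Scored | Apparent benefit, ρ = 1 / 0.5 / 0.3 | Power, ρ = 1 / 0.5 / 0.3 |
|---|---|---|---|
| 50% / 31% | 63 vs 39 | 0.16 / 0.33 / 0.40 | 26% / 41% / 51% |
| 80% / 63% | 100 vs 79 | 0.26 / 0.38 / 0.43 | 65% / 76% / 82% |

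**5. A second model with freely chosen rates.** At ρ = 0.3 to 0.5, the bias against the jelly is 0.09 to 0.15 SD at 90%/70% top-up, 0.18 to 0.30 SD at 90%/50%, and 0.20 to 0.33 SD at 70%/30%. Lost numbers alone leave power for d = 0.5 at 93.7%, 88.3% and 72.0% respectively.

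**6. Direction.** The shift is against the jelly, which is not always towards no effect. With these thresholds and no true effect on the score, the jelly arm would look worse by 0.286ρ at 70% control top-up. Over control rates of 50% to 80% and ρ of 0.3 to 0.5, that is about 0.07 to 0.17 SD.

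**The case against.** The strongest reply is that the sentence also fixes the survey just before the first incision of the stage, an event that occurs with or without a top-up. The reference to re-anesthetizing can be read as ordering the steps, not as a condition, and nothing in the documents excludes un-injected patients. This stands: exclusion is a risk created by the wording, not a stated rule.

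A reader might infer that the jelly's successes vanish from the primary comparison as a whole. The documents do not support that. Injected quantity is also primary and is recorded for each patient, so a patient with no top-up counts as zero added volume. The concern is confined to pain/anxiety and, because they share the timing, to vital signs.

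A reader might also take the fall from 97.6% to about 50% as the expected loss of power. It is not. It assumes that need for a top-up and the score are the same quantity, whereas the score is taken after numbing, so a lower correlation is plausible. Nor does the plan define the test that would lose this power: the Data Analysis Plan calls the primary analyses descriptive, places the tests among secondary analyses and treats repeated rounds as exploratory.

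Finally, scoring un-injected patients as zero for needle-stick pain might seem the obvious repair. That choice partly restates the volume endpoint. For example, assume needle pain with mean 4 and SD 2 in both arms and top-up of 80% versus 50%. Zero-scoring gives means of 0.8 × 4 = 3.2 and 0.5 × 4 = 2.0 (d about 0.49), although pain per stick is identical. It also presumes a needle-stick item that the documents do not show, and gives no rule for anxiety.

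None of this removes the gap. The text can be followed literally, and the volume endpoint does not answer the pain/anxiety objective.

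**Conclusion.** The concern holds as a gap in how the post-dressing pain/anxiety score and vital signs are collected. Followed literally, the Methods would score only topped-up patients and so select on a post-randomisation outcome of the allocated dressing, with bias against the jelly. Under the assumed 70% and 51% top-up, a true 0.5 SD benefit would appear as 0.21 to 0.41 SD, with power of about 50% to 73% against 97.6%; the lower end is a worst case. Selection matters more than lost numbers unless top-up in the jelly arm is low. These sizes rest on assumed top-up rates, an assumed correlation, a normal selection model and a post-dressing return for all 125 per arm. The documents do not show that un-injected patients will in fact be left out.

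**What to change.** In Methods, replace the timing sentence with: *At every return, whether or not lidocaine/epinephrine is injected, vital signs are recorded and the Pain/Anxiety survey is administered immediately before the first incision, and top-up yes/no is recorded.*

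In the Data Analysis Plan, add: *The between-group pain/anxiety comparison includes all randomised patients with a post-dressing return, regardless of top-up. Any comparison restricted to re-injected patients is descriptive only.*

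A needle-stick burden score, with zero when no injection was given, may be pre-specified as a supportive analysis. It should not be the mandatory primary score.

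The cost is protocol wording and a few extra short surveys from patients already in the room. It changes no treatment. Scores not collected at the time cannot be recovered later.

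### Vital signs are described only after re-anesthesia and without a baseline, so the planned arm comparison is a valid total effect of the jelly but cannot separate pain or anxiety from any direct effect of that visit's injected drug

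*Combined protocol and SAP*

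**What the plan says.** The Methods section describes two assessments before the first stage. The first is "All patients will receive a pre-treatment baseline pain/anxiety survey followed by an initial lidocaine injection". The second is "All patients will complete a second pain/anxiety survey immediately after numbing but prior to the first stage of surgery". Both are surveys; vital signs are mentioned at neither.

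At each later stage pain sensation is checked first, and "additional lidocaine/epinephrine will be injected if needed". Then: "After the surgical site is re-anesthetized, vital signs will be recorded", with the survey given at the same point, just before cutting begins. This is the only vital-sign time point in the document.

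Under Research Question and Aims, the hypothesis is that supplementing with jelly "will decrease the overall quantity of lidocaine/epinephrine injectable used". The Endpoints section lists "Blood pressure and heart rate" as secondary. The Data Analysis Plan names heart rate and blood pressure as biometric indicators next to pain and anxiety. It compares the arms on vital signs with simple tests such as the t-test and Wilcoxon rank-sum, and describes no adjustment for a starting value or for the amount injected.

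**The concern.** If the jelly works as hypothesised, fewer jelly patients, or jelly patients with smaller volumes, will have had an epinephrine-containing injection just before the reading. Any direct effect of that drug on heart rate or blood pressure then falls unequally on the two arms, and the imbalance grows with the jelly's success. A difference in vital signs could come from less pain and anxiety, from less injected drug, or from both, and the single planned reading cannot tell these apart.

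The missing baseline is a separate and smaller matter. Randomisation means that its absence causes no bias, but stable differences between patients in blood pressure and heart rate stay in the error term. What is at stake is the interpretation and precision of a secondary endpoint.

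**Working it through.** **The plan's own figure.** The Power Statement claims at least 90% power with 125 per arm for d = 0.5 at p < .05 (two-sided assumed). For the t-test, the noncentrality is 0.5 × √(125/2) = 3.95 on 248 df, which gives power of 97.6%. The claim holds as a lower bound. It is not about timing, and the documents contain no figure for the effect of an injection on vital signs.

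**Inputs for the illustration**
- From the documents: 125 per arm; reading after re-anesthesia; injection only where needed; less injectable hypothesised in the jelly arm.
- Assumed: 80% of control and 50% of jelly patients are re-injected before the reading; the injected drug shifts the reading by 0.5 or 1 SD; pain and anxiety have no effect on the reading.

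**Arm difference from the injection alone** = shift × (0.80 − 0.50)
- 0.5 SD × 0.30 = 0.15 SD
- 1 SD × 0.30 = 0.30 SD

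**Chance of p < .05**, two-sided t-test, noncentrality = d × √(n/2)

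| n per arm | d | Noncentrality | Chance of p < .05 |
|---|---|---|---|
| 125 | 0.15 | 1.19 | 21.9% |
| 125 | 0.30 | 2.37 | 65.6% |
| 60 (assumed) | 0.15 | 0.82 | 12.9% |
| 60 (assumed) | 0.30 | 1.64 | 37.1% |

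The rows at 60 per arm are there because the reading belongs to subsequent stages only. If a return for reconstruction is not counted as a stage, fewer than 125 per arm will contribute.

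These figures hold the SD at 1. If the mix of injected and uninjected patients is allowed to widen the SD, the 125-per-arm figures become about 21% and 58%.

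**Wider range.** With a re-injection difference of 10 to 50 percentage points and a shift of 0.25 to 1 SD, the arm difference runs from 0.025 to 0.50 SD and the chance of significance from about 5% to 98% at 125 per arm. The effect could be negligible or dominant.

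**What a baseline does.** With correlation r between baseline and follow-up, ANCOVA cuts residual variance by r²: 0.5² = 25% and 0.7² = 49%.

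**What a baseline does not do.** A simulation used 80% versus 40% re-injected, a 0.5 SD shift, correlation 0.6, 125 per arm and no pain or anxiety effect (all assumed except the 125):

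| Reading | Baseline covariate | Mean arm difference | p < .05 |
|---|---|---|---|
| After re-injection | No | −0.20 SD | 34% |
| After re-injection | Yes | −0.20 SD | 47% |
| Before re-injection | No | about 0 | 5% |
| Before re-injection | Yes | about 0 | 6% |

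Adjustment leaves the difference where it was and only estimates it more precisely. The earlier reading removes it. The simulation assumes that nothing carries over from earlier injections.

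**The case against.** The strongest reply is that the needle stick belongs to the question. The second objective concerns pain and anxiety tied to anesthesia injections, so if the jelly spares a patient a stick and vital signs differ as a result, that is the benefit the trial is looking for. This stands. The needle-stick response should not be treated as contamination; only a direct effect of the drug counts as such. It also means that simply moving the reading before re-injection would lose something the trial wants, and would part it from the survey.

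Four further points stand:
- Injection is conditional on need, so some readings will follow no re-injection. This does not remove the problem, because need is itself expected to differ by arm.
- Randomisation protects the comparison as a total effect of the jelly.
- The documents never say outright that vital signs stand for pain or anxiety; the hypothesis is about self-reported scores. Listing vital signs as indicators beside those scores does invite that reading.
- The documents do not say that the injected drug changes heart rate or blood pressure, or by how much.

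A reader might infer that the vital-sign endpoint is biased or can support no conclusion, or that the missing baseline invalidates it. The documents do not support either. The total-effect comparison is sound, and a missing baseline in a randomised trial costs precision, not validity.

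**Conclusion.** The point holds as a limit on interpretation. As described, the comparison of blood pressure and heart rate estimates the jelly's total effect, and it cannot separate pain or anxiety from a direct effect of that visit's injection.

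The size of the problem is unknown. The central illustration, 0.15 to 0.30 SD, rests entirely on the assumed 80% versus 50% re-injection and the assumed 0.5 to 1 SD shift. It shows that the effect could matter, not that it does. This is a cheap improvement to a secondary endpoint, worth making before enrolment because a reading not taken cannot be recovered.

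**What to change.** 1. Take one blood pressure and heart rate reading with the pre-treatment baseline survey, and compare arms by ANCOVA with that reading as covariate. This gains precision but does not by itself remove the mixing.
2. Add a reading at the existing pain-sensation check, before any re-injection. Name the first-return pre-injection reading as the comparison that is free of that visit's injection. It may still carry effects of earlier injections.
3. Keep the planned post-anesthesia reading taken with the survey, since the response to the needle stick belongs to the second objective. Report it as a total effect, next to the volume injected at that stage.
4. State in the Data Analysis Plan what each reading is meant to show.

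The cost is protocol wording, one extra reading per patient at baseline and one extra reading per subsequent stage. Only measurement times change; the anesthesia given does not.

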### Resources:

Biostatistician [REDACTED], PhD will perform statistical analyses.

## Subject Information

*Target accrual is the proposed total number of subjects to be included in this study at Mayo Clinic. A "Subject" may include medical records, images, or specimens generated at Mayo Clinic and/or received from external sources.*

Target accrual: 250

Subject population (children, adults, groups): males and females ages 18 and older

Inclusion Criteria: Patients undergoing Mohs surgery anywhere on the nose.

Exclusion Criteria: Patients undergoing multiple Mohs surgeries in different anatomic locations on the same day (nose and ear, etc.). Patients who are unable to consent to the study or who are unable to complete the questionnaire. Patients with allergy to lidocaine.

### Research Activity

Check all that apply and complete the appropriate sections as instructed.

1.  **Drug & Device:** Drugs for which an investigational new drug application is not required. Device for which (i) an investigational device exemption application is not required; or the medical device is cleared/approved for marketing and being used in accordance with its cleared/approved labeling. (Specify in the Methods section)
2.  **Blood:** Collection of blood samples by finger stick, heel stick, ear stick, or venipuncture.
3.  **Biological specimens other than blood:** Prospective collection of human biological specimens by noninvasive means that may include: urine, sweat, saliva, buccal scraping, oral/anal/vaginal swab, sputum, hair and nail clippings, etc.
4.  **Tests & Procedures:** Collection of data through noninvasive tests and procedures routinely employed in clinical practice that may include: MRI, surface EEG, echo, ultrasound, moderate exercise, muscular strength & flexibility testing, biometrics, cognition testing, eye exam, etc. (Specify in the Methods section)
5.  **Data** (medical record, images, or specimens): Research involving use of existing and/or prospectively collected data.
6.  **Digital Record:** Collection of electronic data from voice, video, digital, or image recording. (Specify in the Methods section)
7.  **Survey, Interview, Focus Group:** Research on individual or group characteristics or behavior, survey, interview, oral history, focus group, program evaluation, etc. (Specify in the Methods section)

NIH has issued a *Certificate of Confidentiality* (COC). *When checked, provide the institution and investigator named on the COC and explain why one was requested.* \_\_\_\_\_

### Biospecimens – Categories 2 and 3

(2) Collection of blood samples. When multiple groups are involved copy and paste the appropriate section below for example repeat section b when drawing blood from children and adults with cancer.

a. **From healthy, non-pregnant, adult subjects who weigh at least 110 pounds.** For a minimal risk application, the amount of blood drawn from these subjects may not exceed 550ml in an 8 week period and collection may not occur more frequently than 2 times per week.

Volume per blood draw: \_\_\_\_\_ ml

Frequency of blood draw (e.g. single draw, time(s) per week, per year, etc.) \_\_\_\_\_

b. **From other adults and children considering age, weight, and health of subject.** For a minimal risk application, the amount of blood drawn from these subjects may not exceed the lesser of 50 ml or 3 ml per kg in an 8 week period, and collection may not occur more frequently than 2 times per week.

Volume per blood draw: \_\_\_\_\_ ml

Frequency of blood draw (e.g. single draw, time(s) per week, per year, etc.) \_\_\_\_\_

(3) Prospective collection of biological specimens other than blood: \_\_\_\_\_

### Review of medical records, images, specimens – Category 5

**For review of existing data:** provide a date range or an end date for when the data was generated. The end date can be the date this application was submitted to the IRB. Example: 01/01/1999 to 12/31/2015 or all records through mm/dd/yyyy.

